1.2 Stages in the Adaptive Ttrial

Each new intervention represents a new stage in the adaptive design clinical trial. In order to clearly convey the protocol elements, interventions, objectives, and endpoints for each stage, common elements are described in the main protocol document while each stage is described in a stage-specific appendix.

The stages in the clinical trial include:

- **BET-A:** Risankizumab/Remdesivir vs Placebo/Remdesivir
- **BET-B:** Lenzilumab/Remdesivir vs Placebo/Remdesivir
- **TBD**

1.3 Schedule of Assessments

Table 3. Schedule of Assessments (SOA)*

Day +/- Window	Screen	Baseline	Study Intervention Period	Follow-up Visits		
	-1 or 1	1	Daily until hospital discharge	15 ⁶ ± 2	22 ⁹ ± 3	29 ⁶ ± 3
ELIGIBILITY						
Informed consent	X					
Demographics & Medical History	X					
Targeted physical exam	X					
Review SARS-CoV-2 results	X					
STUDY INTERVENTION						
Randomization		X				
Administration of investigational agent		Detailed in the stage specific appendix.				
STUDY PROCEDURES						
Vital signs including SpO ₂		X ³	Daily until discharge	X		X
Clinical data collection ¹		X ³	Daily until discharge	X	X	X
Adverse event evaluation		X ³	Daily until discharge	X	X	X
Concomitant medication review		X ³	Detailed in the stage specific appendix			
SAFETY LABORATORY						
Safety hematology, chemistry, and liver tests ⁴	X ²	X ³	Day 3, 5, 8, 11 (all ± 1 day) if hospitalized ⁵	X		X
Pregnancy test for females of childbearing potential	X ²					
RESEARCH LABORATORY						
Blood for plasma to test for PCR SARS-CoV-2		X ³	Day 3, 5, 8, 11 (all ± 1 day) if hospitalized			
Oropharyngeal swab ⁷		X ³	Day 3, 5, 8, 11 (all ± 1 day) if hospitalized	X		X
Blood for plasma/serum (primary research) ^{5,8}		X ³	Day 3, 5, 8, 11 (all ± 1 day) if hospitalized	X		X
Blood for serum (secondary research)		X ³	Day 3, 5, 8, 11 (all ± 1 day) if hospitalized	X		X
Blood for plasma for proteomic analysis		X ³	Day 3, 8 (all ± 1 day) if hospitalized	X		X
Blood for RNA		X ³	Day 3, 8 (all ± 1 day) if hospitalized	X		X
Blood for PBMC ¹⁰		X ³	Day 3, 8 (all ± 1 day) if hospitalized	X		X

Notes:

¹ Refer to [Section 8.1](#) of the main protocol document for details of clinical data to be collected including ordinal score, NEWS, oxygen requirement, mechanical ventilator requirement, etc.

² Screening laboratory tests include: ALT, AST, creatinine (and calculate an estimated glomerular filtration rate (eGFR) the formula used is determined by the sites, but should be consistent throughout the study), and urine or serum pregnancy test for females of child-bearing potential. Laboratory tests performed as part of routine clinical care in the 48 hours prior to enrollment will be accepted for determination of eligibility.

³ Baseline assessments should be performed prior to first study product administration. Laboratory tests performed as part of routine clinical care in the 24 hours prior to first dose will be accepted for the baseline laboratory tests. Baseline may be the same as the screening laboratory tests if obtained in the 24 hours prior to first dose.

⁴ Safety laboratory tests include WBC with differential, hemoglobin, platelets, creatinine, total bilirubin, ALT, AST, and INR.

⁵ Any laboratory tests performed as part of routine clinical care within the specified visit window can be used. Window during the 10 days of dosing is ± 1 day.

⁶ In-person visits are preferred but recognizing quarantine and other factors may limit the subject's ability to return to the site for the visit. In this case, the visit may be performed by phone.

- If still hospitalized at Day 15 and 29 or returns to the site for an in-person visit: assess adverse events, collect clinical data (ordinal and NEWS), vital signs, safety laboratory tests, and research laboratory samples (OP swab and blood) as able.
- If phone call only on Days 15 and 29 and all Day 22 visits: assess adverse events, clinical status (ordinal scale), readmission to a hospital, and mortality only.

⁷ Oropharyngeal swabs are preferred, but if these are not obtainable, saliva or nasopharyngeal or nasal swabs may be substituted.

⁸ To include markers of inflammation and coagulation: CRP, ferritin, fibrinogen, d-dimer, troponin.

[figure not shown]
⁹ Day 22 visit performed by phone.

¹⁰ Only collected at selected sites capable of collecting PBMC.

*See SOA in Appendices for study product-specific assessments.

1.4 Study Schema

Figure 1. Study Schema

2. INTRODUCTION

2.1 Study Rationale

A novel coronavirus designated SARS-CoV-2 was first identified in December 2019 in Wuhan, China, and has since spread globally, resulting in an ongoing pandemic of COVID-19. Currently, remdesivir is available under emergency use authorization, but even with the availability of this antiviral the mortality of a hospitalized population with COVID-19 exceeds 7%. Multiple putative therapeutics involving repurposed agents have been proposed, but there is no way to evaluate these numerous agents due to lack of suitable animal models. An adaptive platform trial is one approach to allow for accelerated testing and selection of promising therapeutic agents in order to meet ongoing public health needs.

2.2 Background

2.2.1 Purpose of Study

Coronaviruses (CoVs) are positive-sense, single stranded, enveloped RNA viruses, many of which are commonly found in humans and cause mild symptoms. Over the past two decades, emerging pathogenic CoVs capable of causing life-threatening disease in humans and animals have been identified, namely, severe acute respiratory syndrome coronavirus (SARS-CoV) in 2002-2003 and Middle East respiratory syndrome coronavirus (MERS-CoV) in 2012.

In December 2019, the Wuhan Municipal Health Committee (Wuhan, China) detected an outbreak of viral pneumonia cases of unknown cause. Coronavirus RNA was quickly identified in some patients. This novel coronavirus has been designated as SARS-COV-2. In most (~80%) cases, COVID-19 presents as a mild-to-moderately severe, self-limited acute respiratory illness with fever, cough, and shortness of breath. Symptoms are thought to appear 2 to 14 days after exposure. COVID-19 can be severe, resulting in pneumonia, severe acute respiratory distress syndrome (ARDS), kidney failure, and death. The first US COVID-19 death occurred on February 29, 2020.

On January 30, 2020, the International Health Regulations Emergency Committee of the World Health Organization (WHO) declared the COVID-19 outbreak a Public Health Emergency of International Concern. On January 31, 2020, the US Department of Health and Human Services declared a public health emergency in the United States. On March 11, 2020, the WHO declared the COVID-19 outbreak a pandemic. As of July 2020, more than 10 million cases and half a million deaths had occurred, with forecasting and modeling suggesting that these numbers will continue to rise.

Global efforts to evaluate novel antivirals and therapeutic interventions to treat COVID-19 have intensified. There is currently no vaccine to prevent SARS-CoV-2 infection, and therapeutic agents to treat COVID-19 are limited. The FDA has issued an Emergency Use Authorization for the unapproved product, remdesivir, for the treatment of COVID-19. There remains an urgent public health need for rapid development of novel interventions.

2.3 Risk/Benefit Assessment

Each Appendix will detail the stage and study-specific risk/benefit assessment.

3. OBJECTIVES AND ENDPOINTS

The overall objective of the study is to evaluate the clinical efficacy and safety of different investigational therapeutics relative to the control arm among hospitalized adults who have COVID-19.

See [Table 1](#) in [Section 1.1](#).

4. STUDY DESIGN

4.1 Overall Design

See [Section 1.1](#).

4.2 Rationale for Study Design

This study utilizes an adaptive platform design that increases efficiency to identify safe and efficacious therapeutic agents for patients with COVID-19 during the current outbreak. The platform design allows rapid addition of new therapeutic agents as they are identified and ready for testing in clinical trials. As the study is a multicenter, randomized, controlled study, we will be able to acquire rigorous data about the safety and efficacy of investigational therapeutic agents for COVID-19 that will lead to generalizable evidence. The trial is designed to stop quickly if the agents are unlikely to have a large effect (odds ratio around 1) and will identify those with a large effect (odds ratio 2 or above). This trial is not designed for definitive determination of efficacy, but rather to identify agents for testing in larger definitive studies.

In addition, subject assignment to study intervention will be randomized, which is essential for establishing efficacy of these new therapeutic agents. Finally, collecting clinical and virologic data on enrolled subjects using a standardized timeline and collection instruments should provide valuable information about the clinical course of and morbidities associated with COVID-19 in a diverse group of hospitalized adults.

4.3 Randomization

Randomization will be stratified by study site and severity (baseline Ordinal Score 4 and 5 combined versus Ordinal Score 6 and 7 combined).

While the trial is enrolling patients into multiple active interventions, randomization will be a 2-stage process. In stage 1, a patient who is eligible for 3 interventions A, B, C, will be randomized equally (33% chance) to A, B, and C. At stage 2, the patient will be randomized to active or placebo version of the intervention selected in stage 1 with a 75% or 25% chance, respectively. More generally, patients will first be randomized to 1 of the interventions to which they are eligible with equal allocation. Then patients are randomized to the active or placebo version of that intervention with allocation $k:1$, where k is the number of interventions for which a subject is eligible. For example, if a patient is eligible for 3 active treatments that the site is currently randomizing, the patient will be randomized to 1 intervention with a 1:1:1 allocation to the 3 interventions, then randomized to 1 treatment with a 3:1 allocation of active versus placebo. This process results in equal allocation of the 3 intervention arms and the pooled placebo arm.

Differing entry criteria across interventions adds complexity to this process. Patients who are eligible for all 3 interventions will be randomized to A, B, or C in the first stage, and then have a 25% chance of randomization to placebo in the second stage. However, the patient who is not eligible for C will first be randomized to A and B with equal probability, and will have a 33% chance of randomization to placebo in the second stage, leading to equal size A, B, and pooled placebo groups for this stratum of patients. Ultimately, evaluation of A versus placebo would need to only include subjects that were eligible to be randomized to A. The statistical analysis plan (SAP) will provide details.

The previous paragraph refers to a scenario in which the interventions have largely overlapping study populations. However, at some point the trial might study agents for non-overlapping cohorts. For example, there might be one or multiple interventions that are only appropriate for subjects who have a baseline Ordinal Score of 4 or 5, and a completely different set of

interventions that are only appropriate for subjects who have a baseline Ordinal Score of 6 or 7. Since these interventions would occur in non-overlapping cohorts, they can be viewed as two different studies. Thus, the randomization process described above would be implemented separately in the two cohorts. If there were two interventions in the first cohort, randomization would follow as above with $k=2$, and if there were one intervention in the second cohort, randomization would follow in that cohort as above with $k=1$. Since the study populations and interventions would not overlap, all analyses would be conducted completely separately by cohort.

5. STUDY POPULATION

This trial will study putative therapeutics in a hospitalized adult population (≥ 18 years old) with COVID-19. The platform trial will have common inclusion criteria but may be modified for each stage for the unique risk of the study product in that stage. Exclusion criteria are described in each stage-specific appendix.

5.1 Inclusion Criteria

See [Section 1.1](#).

5.2 Exclusion Criteria

Exclusion criteria are described in each stage-specific appendix.

5.3 Specific Populations

The inclusion of vulnerable subjects and exclusion of specific populations need to be customized according to each intervention, with the current understanding of epidemiology and clinical disease. Inclusion and exclusion of specific populations will be described for each stage in the stage-specific appendices.

5.4 Strategies for Recruitment and Retention

5.4.1 Recruitment

It is anticipated that patients with COVID-19 will present to participating hospitals, and that no external recruitment efforts towards potential subjects are needed. Recruitment efforts may also include dissemination of information about this trial to other medical professionals/hospitals.

The IRB will approve the recruitment process and all materials provided prior to any recruitment to prospective subjects directly.

Screening will begin with a brief discussion with study staff. Some will be excluded based on demographic data and medical history (i.e., pregnant, < 18 years of age, renal failure, etc.). Information about the study will be presented to potential subjects (or legally authorized representative) and questions will be asked to determine potential eligibility. Screening procedures can begin only after informed consent is obtained.

5.4.2 Retention

Retention of subjects in this trial is very important for determining the primary endpoint. As such, after hospital discharge, participating subjects will be reminded of subsequent study visits

and every effort will be made to accommodate the subject's schedule to facilitate follow-up within the specified visit window. Additionally, there are many circumstances that influence the ability to obtain outcome information after discharge. Follow-up visits may be conducted by phone if in-person visits are not feasible.

5.4.3 Compensation Plan for Subjects

Compensation, if any, will be determined locally and in accordance with local IRB requirements, and subject to local IRB approval.

5.4.4 Costs

There is no cost to subjects for the research tests, procedures/evaluations and study product while taking part in this trial. Procedures and treatment for clinical care including costs associated with hospital stay may be billed to the subject, subject's insurance or third party.

6. STUDY PRODUCT

Each stage in this platform trial may have different study products. Information about the study product(s) for a given stage can be found in the stage-specific appendix.

7. STUDY INTERVENTION DISCONTINUATION AND SUBJECT DISCONTINUATION/WITHDRAWAL

7.1 Halting Criteria and Discontinuation of Study Intervention

7.1.1 Individual Study Product Halting

See the stage-specific appendix for specific study product stopping rules.

7.1.2 Study Halting

Given the potential severity of COVID-19, there are no pre-specified study stopping rules. Instead there will be close oversight by the protocol team and frequent DSMB reviews of the safety data.

7.2 Withdrawal from the Study

Subjects are free to withdraw from participation in the study at any time upon request, without any consequence. Subjects should be listed as having withdrawn consent only when they no longer wish to participate in the study and no longer authorize the Investigators to obtain their outcome data.

Subjects who withdraw from this study or are lost to follow-up after signing the informed consent form (ICF) and administration of the study product, will not be replaced. The reason for subject withdrawal from the study will be recorded on the appropriate CRF.

7.3 Lost to Follow-Up

A subject will be considered lost to follow-up if he or she fails to appear for all follow-up assessments. In lost to follow-up cases, attempts to contact the subject should be made and these efforts should be documented in the subject's records.

8. STUDY ASSESSMENTS AND PROCEDURES

8.1 Screening and Efficacy Assessments

8.1.1 Screening Procedures

Screening procedures may be done from Day -1 to Day 1. However, in many cases all the screening procedures can be done in less than 24 hours. If that is the case, Day 1 pre-study product administration baseline assessments, specimen collection and the initial study product administration can occur on the same calendar day as the screening procedures.

After the informed consent, the following assessments are performed to determine eligibility and obtain baseline data:

- Confirm the positive SARS-CoV-2 test result (per inclusion criteria).
- Take a focused medical history, including the following information. Additional information may be needed based on risk profile of the study product and the exclusion criteria (e.g., recent live vaccine history). Please consult stage-specific appendix. The minimum history includes:
 - Day of onset of COVID-19 signs and symptoms.
 - History of chronic medical conditions including chronic oxygen requirement prior to onset of COVID-19.
 - History of medication allergies.
 - Medications and therapies for this current illness taken in the 7 days prior to enrollment.
 - Ask if they are participating in another clinical trial or plan to enroll in another clinical trial in the next 30 days.
- Women of childbearing potential should be counseled to either practice abstinence or use at least one primary form of contraception not including hormonal contraception from the time of screening through Day 29. Women should be confirmed to not be breastfeeding.
 - Note: If a woman is either postmenopausal (i.e., has had ≥ 12 months of spontaneous amenorrhea) or surgically sterile (i.e., has had a hysterectomy, bilateral ovariectomy (oophorectomy), or bilateral tubal ligation), she is not considered to be of childbearing potential.
- Height and weight (height can be self-reported).
- Results of most recent radiographic imaging (chest x-ray or CT scan).
- SpO₂ on room air (not needed if on supplemental oxygen, mechanical ventilation, or ECMO).
- Blood for screening laboratory evaluations if not done as part of routine clinical care in the 48 hours prior to enrollment. Additional screening laboratory evaluations may be added based on the risk profile of the study product for a given stage of the study. Please see appendices for stage-specific details. The minimum screening laboratory evaluations include:
 - ALT.
 - AST.
 - Creatinine (and calculate eGFR).

- Any automated calculation by the clinical laboratory or published formula for this calculation is acceptable. The site should select a formula to be used for all subjects enrolled at the site for the duration of the study.
- Urine or serum pregnancy test (in women of childbearing potential).

Clinical screening laboratory evaluations will be performed locally by the site laboratory.

The overall eligibility of the subject to participate in the study will be assessed once all screening values are available. Complete the inclusion and exclusion criteria checklists on the day of enrollment as these forms include data needed to register all potential subjects in the electronic data capture (EDC) system. The screening process can be suspended prior to complete assessment at any time if exclusions are identified by the study team.

Study subjects who qualify will be randomized in the interactive response technology system (IRT) system, and all others will be registered as screen failures only in the EDC system. The study team has 24 hours to complete Day 1 baseline assessments prior to the first study product administration including the collection of OP swab and blood, assessment of the ordinal scale and NEWS and completing or recording a baseline physical examination that was done.

8.1.2 Efficacy Assessments

For all baseline assessments and follow-up visits, refer to the Schedule of Assessments (SOA) for procedures to be done, and details below for each assessment.

Laboratory tests performed as part of routine clinical care in the 24 hours prior to first dose will be accepted for the baseline laboratory tests. Baseline may be the same as the screening laboratory tests if obtained in the 24 hours prior to first dose.

8.1.2.1 Measures of clinical support, limitations and infection control

The subject's clinical status will be captured on each study day while hospitalized up until and including Day 29. If a subject is discharged prior to Day 15, clinical status is captured on Days 15 and 29 as an outpatient if the subject returns for an in-person clinic visit or by phone if an in-person visit is not possible. Clinical status will also be captured on the Day 22 phone visit. Clinical status is largely measured by the ordinal scale and the NEWS. Unlike the NEWS, the ordinal scale can also be evaluated over the phone if the discharged subject is unable to return for in-person visits on Day 15 and 29 as well as on Day 22.

Ideally, the ordinal scale is completed concurrently with the NEW Score just prior to study product administration. The following measures are recorded for the ordinal scale:

- Hospitalization.
- Oxygen requirement.
- Non-invasive mechanical ventilation (via mask) requirement.
- High flow oxygen requirement.
- Invasive mechanical ventilation (via endotracheal tube or tracheostomy tube) requirement.

- ECMO requirement.
- Ongoing medical care preventing hospital discharge (COVID-19 related or other medical conditions).
- Limitations of physical activity (self-assessed).
- Isolated for infection control purposes.

8.1.2.2 Ordinal Scale

The ordinal scale is the primary measure of clinical outcome.

The scale used in this study is as follows:

1. Not hospitalized, no limitations on activities;
2. Not hospitalized, limitation on activities and/or requiring home oxygen*;
3. Hospitalized, not requiring supplemental oxygen* - no longer requires ongoing medical care;
4. Hospitalized, not requiring supplemental oxygen* - requiring ongoing medical care (COVID-19 related or otherwise);
5. Hospitalized, requiring supplemental oxygen*;
6. Hospitalized, on non-invasive ventilation or high flow oxygen devices;
7. Hospitalized, on invasive mechanical ventilation or ECMO;
8. Death.

*For subjects on chronic supplemental oxygen, this pertains to an increased oxygen requirement above baseline.

8.1.2.3 National Early Warning Score (NEWS)

NEWS has demonstrated an ability to discriminate subjects at risk of poor outcomes.¹ This score is based on 7 clinical parameters (see [Table 4](#)). The NEWS is being used as an efficacy measure. The NEWS Score should be evaluated daily while hospitalized and on Days 15 and 29. It can be performed concurrently with the Ordinal Scale. This should be evaluated at a consistent time for each study day and prior to administration of study product. The 7 parameters can be obtained from the hospital chart or electronic medical record (EMR) using the last measurement prior to the time of assessment and a numeric score is given for each parameter (e.g., a RR of 9 is one point, oxygen saturation of 92 is two points). This is recorded for the day obtained (i.e., on Day 3, the vital signs and other parameters from Day 3 are used to obtain NEWS Score for Day 3). ECMO and mechanically ventilated subjects should be assigned a score of 3 for RR (RR <8) regardless of the ventilator setting. Subjects on ECMO should get a score of 3 for heart rate since they are on cardiopulmonary bypass.

Table 4. National Early Warning Score (NEWS)

PHYSIOLOGICAL PARAMETERS	3	2	1	0	1	2	3
Respiration Rate	≤8		9 - 11	12 - 20		21 - 24	≥25
Oxygen Saturations	≤91	92 - 93	94 - 95	≥96			
Any Supplemental Oxygen		Yes		No			
Temperature	≤35.0		35.1 - 36.0	36.1 - 38.0	38.1 - 39.0	≥39.1	
Systolic BP	≤90	91 - 100	101 - 110	111 - 219			≥220
Heart Rate	≤40		41 - 50	51 - 90	91 - 110	111 - 130	≥131
Level of Consciousness				A			V, P, or U

Level of consciousness = alert (A), and non-alert and arousable only to voice (V) or pain (P), and unresponsive (U).

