The primary null hypothesis being tested is that proportions of subjects at each level of the 8-point ordinal scale does not differ at Day 8 between the experimental and control arms. For this, the parameter of interest is the "common odds ratio," which quantifies the shift in the severity distribution resulting from treatment. For an efficacious treatment, an odds ratio greater than 1 quantifies an improvement in disease severity; a value of 2 indicates a bigger improvement than a value of 1.25. The null hypothesis to be tested is that the odds of improvement on the ordinal scale is the same for the placebo and experimental treatment arms (i.e., the common odds ratio is 1). It is worth noting that, for large sample sizes, the test based on the proportional odds model is nearly the same as the Wilcoxon rank sum test.

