9.3.2 Analysis of the Primary Efficacy Endpoint

The ordinal scale will be used to estimate a proportional odds model, with covariate adjustment for baseline steroid use and baseline severity (baseline Ordinal Score 4 and 5 combined versus Ordinal Score 6 and 7 combined). Because of the potential for COVID-19 treatments to emerge, a key supplemental analysis would mimic this primary analysis, but add adjustments for baseline use of each other innovative treatment. The hypothesis test will evaluate whether the common odds ratio for treatment is equal to one. The distribution of baseline steroid (and emerging treatments included in the supplemental analysis) and severity results will be summarized by treatment arm as percentages. Subjects in the shared control arm can only be used in comparison of any given intervention ‘A’, if they were eligible for ‘A’ and consented to randomization to ‘A’; thus controls randomized at clinics where ‘A’ is not currently being studied are not compared to subjects in the ‘A’ arm. Efforts to minimize loss-to-follow-up will be considerable. However, small amounts of missing data may occur. In such cases, subjects without final outcome data will be excluded from the analysis. Sensitivity analyses will evaluate the impact of making different assumptions about missing observations. These analyses will be defined in the SAP.

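### The primary Day 8 model leaves out baseline NEWS, which is already collected before dosing; the analysis is valid, but a possible gain in power of unknown size is forgone

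*Protocol*

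**What the plan says.** Section 9.3.2 specifies a proportional odds model for the Day 8 ordinal score, "with covariate adjustment for baseline steroid use and baseline severity (baseline Ordinal Score 4 and 5 combined versus Ordinal Score 6 and 7 combined". A supplemental analysis adds baseline use of other emerging treatments. That section leaves the missing-data sensitivity analyses to the SAP, but it sets the covariates itself.

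NEWS is available in time. Section 8.1.1 gives the study team 24 hours to complete the Day 1 work before the first administration, "including the collection of OP swab and blood, assessment of the ordinal scale and NEWS". A footnote to the schedule in section 1.3 agrees: "Baseline assessments should be performed prior to first study product administration". Section 8.1.2.3 allows chart extraction, "using the last measurement prior to the time of assessment", and says of the score that "NEWS has demonstrated an ability to discriminate subjects at risk of poor outcomes". Change in NEWS from Day 1 is a secondary endpoint in Table 1, so the baseline value is needed in any case.

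The protocol otherwise uses NEWS only as an outcome. It is not a covariate in section 9.3.2 or a listed subgroup in section 9.3.8.

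**The concern.** The two-level severity factor pools score 4 with 5 and score 6 with 7. NEWS overlaps with it through oxygen and ventilation, but also scores respiratory rate, saturation, temperature, blood pressure, heart rate and consciousness. Its two points for supplemental oxygen separate score 4 from score 5 inside one stratum.

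Two subjects with ordinal score 5 show the difference on Table 4. One on oxygen with otherwise normal values scores 2. Another on oxygen (2) with respiratory rate 26 (3), saturation 92 (2), heart rate 115 (2) and temperature 38.5 (1) scores 10. Given the same steroid use, the planned model treats them alike.

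If NEWS predicts Day 8 status beyond severity, omitting it lowers power. One odds ratio drives the futility rule (below 1 at about 50 per arm), the promising declaration (p<.20) and the significance declaration (p<.05). A trial of this size, meant to find agents with large effects, has reason to use prognostic information it already holds.

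**Working it through.** **1. The plan's own figure.** Section 9.1 and Table 5 give 100 per arm (N = 200), an odds ratio of 2 (λ = ln 2 = 0.693) and control percentages of 0 / 34.6 / 1.2 / 10.6 / 17.1 / 8.8 / 24.2 / 3.5 for categories 1 to 8. Doubling each cumulative odds gives a treated arm of 0 / 51.4 / 1.3 / 10.7 / 14.3 / 6.2 / 14.3 / 1.8. For the average of the two arms, Σp³ = 0.092.

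Rearranging the sample size formula of section 9.1:

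power = Φ( λ·√[N(1 − Σp³)/12] − z )

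λ·√[200 × 0.908/12] = 0.693 × 3.890 = 2.696

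- α = .05: Φ(2.696 − 1.960) = Φ(0.736) = 0.769
- α = .20: Φ(2.696 − 1.282) = Φ(1.415) = 0.921

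A simulation of an unadjusted model with the futility rule (10,000 trials) gave 0.764 and 0.912, with 0.029 stopped for futility. Table 6 states 0.765, 0.913 and 0.028. Table 6 therefore reproduces, as an unadjusted calculation.

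**2. Adding NEWS.** The documents give none of the next inputs, so they are assumptions: 40% of subjects with baseline score 6-7; a severity log odds ratio of 2; a true odds ratio of 2 conditional on severity and NEWS; and a residual NEWS effect β, in log-odds per SD within severity stratum, varied from 0 to 1.0. Outcomes came from a latent-logistic model calibrated so that the control arm reproduces Table 5. Each trial was fitted with treatment and severity, and again with NEWS added. Futility was an estimate below 1 at 50 per arm. Steroid use was not modelled. There were 4,000 trials per setting (Monte Carlo standard error about 0.7 points).

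Each cell shows severity only → severity plus NEWS.

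| β | Median odds ratio | p<.05 | Promising (p<.20) | Futility stop |
|---|---|---|---|---|
| 0 | 2.01 → 2.01 | 73.4% → 73.5% | 89.4% → 89.0% | 3.3% → 3.5% |
| 0.25 | 1.99 → 2.01 | 72.3% → 72.7% | 88.6% → 89.0% | 3.4% → 3.7% |
| 0.5 | 1.94 → 2.01 | 69.1% → 72.4% | 86.8% → 88.9% | 4.3% → 3.7% |
| 0.75 | 1.88 → 2.02 | 64.7% → 71.8% | 84.2% → 88.6% | 5.1% → 4.0% |
| 1.0 | 1.81 → 2.02 | 60.1% → 71.3% | 80.6% → 88.1% | 6.2% → 3.9% |

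Gains at p<.05 are 0.4, 3.3, 7.1 and 11.2 points for β = 0.25, 0.5, 0.75 and 1.0. Gains at p<.20 are 0.4, 2.1, 4.4 and 7.5 points.

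**3. Checks.**
- A separate simulation on the same assumptions (5,000 trials per setting) gave 69.5% → 72.3%, 63.7% → 71.3% and 59.6% → 71.1% at p<.05 for β = 0.5, 0.75 and 1.0. At an odds ratio of 1 the false-promise rate was 9.2% without NEWS and 9.5% with it.
- With a severity log odds ratio of 1 or 3, the gain at p<.05 was about 3 points at β = 0.5 and 11 to 12 at β = 1.0.
- With the severity-adjusted odds ratio set to 2 instead (3,000 trials), power at p<.05 rose from about 72% to 75.5%, 78.5% and 82.9% for β = 0.5, 0.75 and 1.0. The gain does not depend on which odds ratio is taken as the truth.
- With β = 0, severity alone raised power at p<.05 from 59.0% (no covariates) to 73.4%. Under these assumptions the planned model already recovers most of what adjustment can offer when NEWS is weak.

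**The case against.** The strongest reply is that the plan contains no error. Adjusting for the severity stratification factor and steroid use is conventional, the type I error is unaffected, and NEWS has a stated role as an efficacy measure. This stands: the point concerns efficiency only.

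A reader might infer that the planned odds ratio is biased toward 1. The documents do not support that. The odds ratio is non-collapsible, so the planned estimate lies nearer 1 only relative to a NEWS-conditional odds ratio that the protocol does not target. Nor does it follow that follow-on trials would receive a faulty estimate. A NEWS-conditional odds ratio would be too optimistic for sizing a trial analysed without NEWS.

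The size of the gain is assumed. The sentence in section 8.1.2.3 is general and says nothing about prognosis within severity strata. The larger gains need β of 0.75 to 1.0, for which the protocol gives no support; at 0.25 the gain is negligible. This stands, and it limits the conclusion.

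The simulated comparator omits steroid use, so any overlap between steroid use and NEWS is credited to NEWS. Part of the gain may also come from undoing the severity dichotomy, and a four-level baseline ordinal score was not tested. Both are fair limits on the size.

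A single slope is open to question because "ECMO and mechanically ventilated subjects should be assigned a score of 3 for RR", whatever the ventilator setting, and subjects on ECMO receive a fixed heart-rate score. That is a cost to check in a sensitivity analysis.

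A reader might also infer that NEWS must be re-extracted from before randomization, since section 8.1.1 allows scoring after it. Values taken before dosing in a double-blind trial are legitimate, and re-extraction could create a second baseline beside the one used for change from Day 1.

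**Conclusion.** The point holds as an avoidable and possibly small loss of efficiency. At β = 0.25 it is negligible; at 1.0 it reaches about 11 points at p<.05 and 8 at p<.20. False futility stops change clearly only at the strongest assumed effect, from about 6% to 4%. These figures rest on a true conditional odds ratio of 2, 40% severe at baseline, a severity log odds ratio of 2, no steroid term and no missing data. The direction is secure whenever NEWS predicts outcome beyond the planned covariates; the size cannot be fixed from the protocol. The case for change rests on the asymmetry: a possible gain against essentially no loss in power or in control of false-promise declarations.

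**What to change.** In section 9.3.2:

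- Add pre-dose Day 1 NEWS as a pre-specified linear covariate beside steroid use and severity.
- Use the same model at the interim and final looks, and in the later-day ordinal analyses of section 9.3.3.
- State that the treatment odds ratio is then conditional on NEWS.
- Give a simple rule for missing baseline NEWS so that no subject is dropped, for example the mean of the subject's severity stratum with arms pooled.
- Report the model without NEWS as a sensitivity analysis.

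The time-to-recovery analysis can stay as planned. The cost is a short addition to section 9.3.2, with no new data, visits or subjects. The statistical price is one extra parameter, a linearity assumption that includes the fixed scores for ventilated and ECMO subjects, and an odds ratio that should not be used to size a follow-on trial analysed without NEWS. For that purpose the sensitivity analysis supplies the estimate without NEWS.
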